Data Analysis & Interpretation: We will analyze qualitative interview data using atlas.ti, qualitative data analysis software, and the quantitative data using the SPSS version 24. We will start by coding, a process in which quotes are marked and labeled. The labeled quotes are then sorted and grouped, so that categories, then concepts, then themes can be developed. As is often standard practice for qualitative data analysis, analysis will be concurrent with data acquisition. Quantitative data will be examined initially for missing values. The primary aims of our data analytic strategy will be directed toward the adherence, retention and any guidance to inform modification of our method. We will focus our analyses on a feasibility of conducting a larger study and report our findings with this limitation in mind. Our goal is to collect important data regarding our method, our ability to implement recruitment strategies, and the feasibility of the treatment and measurements. Information derived from our research will lead to better-designed full-scale studies and informed decisions regarding whether it is worthwhile to commit additional resources to future treatment development. For quantitative data, descriptive statistics will be used to summarize the variables as well as detect outliers and data entry errors. When applicable, normality of the distribution will be examined for outcome variables. Chi-squared and Analysis of Variance will be used to assess the effectiveness of the randomization procedures by comparing participants in each treatment condition on baseline variables. Due to our small sample size our statistical analytical finding will be interpreted with caution. Other preliminary analyses will include evaluation of patterns of missing data, dropout rates, distributional properties of variables, and correlations among measures. Although there are important limitations associated with the analysis of our data, we do propose to conduct limited statistical analyses. First, keeping in mind the theoretical and practical issues reviewed above, all analyses will be considered preliminary. We will calculate an estimated effect size for our primary outcome, though it will be interpreted with caution, and in the context of the 95% confidence interval that surrounds it. It will also be interpreted within the context of other important information such as the clinical significance of study findings, and existing data from prior relevant research studies. For aims 2-3, All potential covariates (e.g., age, duration of cancer) will be summarized with descriptive statistics and graphs to determine whether a continuous, categorical, or interval representation is most appropriate. Second, effect of any systematic differences between dropouts and completers will be explored by including the variable of concern to the model as a covariate. Third, any comparison can be adjusted for subject-specific characteristics (e.g., covariates found in initial analyses). Furthermore, group by time interaction will be included in all models. For Aim 2-3, descriptive statistics and exploratory graphing such as frequencies, means, standard deviations, box and whisker plots, stem and leaf diagrams, and scatter plots will be used to assess normality of the data. If necessary, the continuous outcome data will be transformed appropriately. Prior experience leads us to expect that for all variables, the distributions will be skewed and the variances will not be homogeneous. Similarly, potential covariates will be summarized with descriptive statistics and graphs to determine whether a continuous, categorical or an interval representation is the most appropriate approach. Missing data will be examined to assess randomness. Analysis of variance will be used to test our hypothesis. We will adjust pvalues for multiple testing using a Bonferroni correction. Data will be analyzed using a Mixed Effect Model. This method allows the inclusion of subjects with missing data or those who terminated early without relying on data imputation procedures. Denominator degrees of freedom will be calculated using the Kenward-Roger small sample correction. Data will be analyzed from all randomized subjects for whom we have a baseline assessment and at least one post-baseline evaluation. Effect of these mediator variables will be tested using the same mixed model. To test for mediation effect, we will utilize the analytic strategy. The multiple-mediation model includes a multiple-path mediating effect through both mediators which allows one mediator to causally affect the other. We will conduct a Sobel testnto check for significant mediation. Next, we will use the formula provided by MacKinnon to determine the percentage of the intervention condition to primary outcome path that was accounted for by change in our mediator. Based on our ongoing studies, we expect a dropout rate of <10% after baseline assessment. Primary outcomes will be tested using an intent-to-treat framework. The data will be analyzed by a "Mixed Effect Model." As we mentioned above, due to our small sample size our statistical analytical finding will be interpreted with caution.

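### With 10 patients per arm, the planned percentage mediated is too unstable to report as a single figure and a non-significant Sobel test says little; descriptive intervals would be a text-only improvement

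*Combined protocol and SAP*

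**What the plan says.** The plan is in Section 9, under Data Analysis & Interpretation. It introduces mediators without naming them: "Effect of these mediator variables will be tested using the same mixed model". It then describes their structure: "The multiple-mediation model includes a multiple-path mediating effect through both mediators which allows one mediator to causally affect the other". The test follows: "We will conduct a Sobel testnto check for significant mediation". A cited formula, not printed, is then used "to determine the percentage of the intervention condition to primary outcome path that was accounted for by change in our mediator".

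Other statements in the same section bear on this:

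- The only 95% confidence interval planned is for the effect size on the primary outcome.
- On the models: "Furthermore, group by time interaction will be included in all models".
- On multiplicity: "We will adjust pvalues for multiple testing using a Bonferroni correction". The number of tests is not given.
- On the data, the authors expect that "the distributions will be skewed and the variances will not be homogeneous".
- On status: "all analyses will be considered preliminary".

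The sample is 20 men assigned 1:1 (Section 9, Patient Recruitment; Section 10). Section 9.8 lists two primary symptom scores, IIEF-5 and ICIQ.

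**The concern.** A percentage mediated is a ratio whose denominator is the estimated total treatment effect. With 10 patients per arm that denominator can lie near zero or take the wrong sign, and the ratio then becomes very large or negative. The plan would print it as one number with no interval. The Sobel test multiplies two imprecisely estimated paths, so a non-significant result could easily be misread as evidence against the mechanism.

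The pilot is meant to inform a decision on a larger study, so a stray mechanism figure could be carried forward. The analysis also cannot be run as written. The mediators are not named, the primary outcome could be either symptom score, and no visit or time lag is given.

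**Working it through.** **Inputs from the documents.** 20 patients, 1:1, so 20/2 = 10 per arm. Two sensitivity cases: 24 patients (12 per arm; the recruitment target under Feasibility Outcomes) and 18 (9 per arm; 20 less the 10% upper limit on expected dropout). The documents give no path sizes and no power or precision for mediation, so there is no stated figure to reproduce.

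**Assumptions.** Two-sided 5% level. In SD units, a is the effect of arm on mediator, b the effect of mediator on outcome given arm, and c' the direct effect. The percentage is ab/(ab + c').

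- Set 1: (0.5, 0.4, 0.3), true value 0.20/0.50 = 40%
- Set 2: (0.8, 0.5, 0.4), true value 0.40/0.80 = 50%
- Set 3: (1.0, 0.6, 0.4), true value 0.60/1.00 = 60%

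**Hand check, 10 per arm, one value per variable, unit residual variances.**

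- SE(a) = √(2/10) = 0.447. SE(b) ≈ √(1/16) = 0.25, since the mean of 1/χ² on 18 df is 1/16.
- Sobel SE = √(a²·SE(b)² + b²·SE(a)²). Set 2: √(0.64×0.0625 + 0.25×0.2) = √0.09 = 0.30, so ab/SE = 0.40/0.30 = 1.33. Sets 1 and 3 give 0.92 and 1.64. All are below 1.96.
- SE(total) = √((1 + b²)×2/10). Set 2: √(1.25×0.2) = 0.50, so total/SE = 0.80/0.50 = 1.6, and the estimated total effect is negative in about 5.5% of trials. Sets 1 and 3 give 1.04 and 1.92, or about 15% and 2.8% negative.

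**Simulation** (normal errors; 20,000 runs per one-value cell, 3,000 per four-visit cell; four-visit ranges cover within-patient correlation 0.3 to 0.7). Entries are for sets 1 / 2 / 3.

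| Model | Percentage outside 0-100% | Sobel power |
|---|---|---|
| One value, 10 per arm | 36 / 26 / 24% | 2 / 9-10 / 22% |
| One value, 9 per arm | 38 / 28 / 26% | 2 / 7 / 17% |
| One value, 12 per arm | 33 / 22 / 20% | 3 / 14 / 32% |
| Four visits, group-by-time, read at week 13 | 31-32 / 21-22 / 20-21% | 8-10 / 31-34 / 53-55% |
| Four visits, constant effect | 20-28 / 11-19 / 12-16% | 13-22 / 42-63 / 65-86% |

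**Spread of the percentage when the truth is 50%** (middle 95% of estimates):

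- one value: about -130% to above 300%
- group-by-time: -195% to 297% at the widest
- constant effect: 11% to 187% at best

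**Bonferroni.** If the correction covers the Sobel test for two symptom scores (level 0.025), one-value power drops to 0.7 / 4 / 11%.

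**False-positive rate of the Sobel test, nominal 5%:**

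- One value, normal errors: about 0.05% when both paths are zero, rising to 2.9% when one is zero and the other large (a up to 1.5, b up to 1.0).
- One value, skewed errors (lognormal, log-SD 0.75) with a 2:1 SD ratio between arms: up to 5.8%, at a = 1.5, b = 0.
- Four visits, normal errors: 0 to 5.8%.

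**The case against.** **The plan already urges caution.** It calls every analysis preliminary, and mediation appears neither in the aims nor among the feasibility outcomes. That stands and keeps the point minor. It does not make a bare percentage informative when its denominator may be close to zero.

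**The power figures rest on assumed paths.** That also stands. Power runs from 2% to 86% across the models tried, so a reader should not infer that the Sobel test is underpowered whatever the truth. Nor does high power rescue the ratio: in the best constant-effect cells at least 11% of percentages still fall outside 0 to 100%.

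**Stronger readings to avoid.** A reader might infer that the Sobel test is always conservative here. That fits small paths with one value and normal errors, but not four visits or the skewed, unequal-variance data the plan expects, where null rejection reaches 5 to 6%. The plan does allow transformation, which could reduce that skew. The opposite inference, a serious false-positive problem, is not supported either.

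A reader might also infer a separate significance test of the path through both mediators. The text describes that path as part of the model and then plans one Sobel test; it does not say the three-step product is tested.

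**Timing.** One might conclude that no mediator can precede the outcome. The visible text does not show that, and the timeline figure is not available. Under TPMS Treatment, Doppler and symptom scores are listed at baseline and weeks 4, 8, 13 and 24. Under Patient Recruitment, symptom scores, MRI and blood flow are given at baseline and end of study. So blood flow has earlier visits, while the visible text shows no mid-treatment MRI.

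**Conclusion.** The point holds, as a minor one. At 10 per arm the percentage mediated is too unstable to interpret as a single figure. It is nonsensical (below 0 or above 100%) in roughly a quarter to a third of trials with one value per variable, and in 11 to 32% with four visits; 18 or 24 patients does not cure this. A non-significant Sobel result would say little, because power is low under most of the path sizes and models tried. The error rate of the test is not the main problem.

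This rests on assumed path sizes, on reading the unprinted formula as indirect over total effect, and on a visit schedule taken without the timeline figure. The unnamed mediators, outcome score and visits are gaps whatever the numbers.

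**What to change.** Delete the percentage mediated and the Sobel significance statement. In their place:

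1. For each named mediator, report the baseline-adjusted difference between arms, and the mediator-outcome association adjusted for arm and for baseline mediator and outcome. Give each a 95% confidence interval and label both descriptive.
2. If an indirect effect is reported, including any path through both mediators, give a Monte Carlo or bootstrap 95% interval and make no significance claim.
3. Name the mediators, the outcome score and the visits. The blood-flow and muscle mechanisms in Section 7 are the natural candidates, though it does not call them mediators. Subject to the timeline figure, Doppler at week 4 or 8 can precede the week 13 score. For an MRI mediator with no visit before the outcome, report only the arm difference.

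The cost is text only; sample size, visits and data are unchanged. The trial gives up a formal mediation claim, and the intervals will be wide. For the arm difference the half-width is about 2.11 × √(2/10) × √(1 − r²), which is 0.94 SD at baseline correlation r = 0 and 0.67 SD at r = 0.7. Allowing for chance baseline imbalance gives about 0.95 and 0.68. For the association it is about 0.53 SD per SD. The Monte Carlo interval is only approximate: with skewed errors and a 2:1 SD ratio it excluded zero in up to about 7% of null trials, which is why it should carry no significance claim.

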### **Section 9.4 Devices**

9.4) For each research device, state the status of the device, the PI's determination as to whether the device is a significant or non-significant risk device, and provide justification for this determination. A copy of determinations from the FDA should be attached. - Also, for investigational devices describe how and by whom the device will be received, stored, secured and dispensed.

Magnetic Stimulation device is a device that is FDA approved for both peripheral and CNS stimulation. The FDA approved applications for this specific model Magpro R30 model is to treat depression. The proposed application i.e. improving blood flow and strengthening pelvic muscles in post-prostatectomy men is an off-label use. This device generates magnetic pulses whose amplitude and frequency can be controlled. The device is non-invasive and has been shown to be safe with no side effects. When a muscle is stimulated it can cause slight tingling. It is commercially available for clinical use and is being used in Anesthesiology and Psychiatry at the San Diego VA Hospital for pain management and depression therapy. Doppler device is also standard non-invasive FDA approved device used for imaging in cardiology and radiology to measure blood flow in blood vessels/tissue.We determined that the magnetic stimulation device is a non-significant risk device based on FDA guidance provided in the link: https://www.fda.gov/media/75459/download

### **Section 9.8 Questionnaires & Surveys**

9.8) Provide the name and a reference for questionnaires/surveys that are standard or identify them here and attach a copy of the questionnaire/survey. Questionnaires or surveys that are not clinical standard references must be uploaded. Reference the help link for additional information related to surveys administered to VA personnel and approved platforms for web-based surveys.

Primary symptom scores will be assessed using International Index of Erectile Function (IIEF-5) and International Consultation of Incontinence Questionnaire (ICIQ) symptom scores. Both of these questionnaires will take about 15-20 minutes to answer. Both questionnaires will be given in hard copy only. Electronic copies of these questionnaire have been attached to the application.

9.9) Provide a Data Safety Monitoring Plan (DSMP) or the details of a Data Safety Monitoring Board; if a written plan is available, attach a copy of the plan to the submission form.

This is a feasibility study using an non-invasive, previously FDA approved device. We will monitor for any adverse effects and report these to the IRB within 5 days following the guidelines provided in our internal policy (SOP Document 67) -Adverse event /unanticipated outcome. Local Research Deaths. We ensure oral notification of the Institutional Review Board (IRB) immediately upon becoming aware of any local research death that is both unanticipated and related to the research.

Local Serious Adverse Event (SAEs). We will ensure written notification of the IRB within 5 business days after becoming aware of any local SAE that is both unanticipated and related to the research.

Serious Problems. We will ensure written notification of the IRB within 5 business days after becoming aware of any serious problem that is both unanticipated and related to the research.

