### Section 7 - Background and Significance

### 7) Provide a succinct discussion of relevant background information to justify performing the proposed study.

Literature suggests that prostate cancer is the most common type of cancer in men over 50 years old, with an estimated 218,000 new cases each year. This cancer's incidence is especially prevalent (29%) among VA patients . Surgical therapy for prostate cancer is a significant risk factor for urogenital complications which dramatically affect the quality of life for male Veterans, such as erectile dysfunction (ED), or the inability to initiate or maintain adequate erection for intercourse, and urinary incontinence 20-80% of these men will never regain normal erectile function and 31% will have urinary incontinence. Transpelvic magnetic stimulation (TPMS) for Urogenital and Pelvic Floor Disorders: Recently, TPMS therapy has been recognized as beneficial in treating nerve and muscle injuries. TPMS acts by strong pulsing magnetic fields that depolarize neural elements, resulting in improved muscle contraction. Repetitive contraction and relaxation of normal skeletal muscle results in increased muscle strength, endurance, and circulation. Previous studies showed beneficial effects of TPMS in UI in females. However, these studies were inconclusive. Apparently, these clinical studies attempted to reverse the established neuropathy and muscle dysfunction in symptomatic patients. Our proposed studies will evaluate the preventive potential of TPMS in acute neuropraxia related penile and sphincter muscle dysfunction. Recent reports showing efficacy of TPMS for skeletal muscle regeneration after surgical trauma clearly supports our claim. TPMS does not cause adverse effects but improves muscle function by minimizing post-injury inflammation, atrophy and scar formation. Based on published reports and taking advantage of muscle regeneration potential, we propose TPMS after surgery (as acceptable to the urologic surgeon) to enable systematic evaluation of its potential to prevent muscle dysfunction, i.e., immediate muscle recovery prior to fibrosis onset (never attempted before). Furthermore, TPMS treatment will lead to muscle strengthening. In addition, low intensity (5-10% amplitude) TPMS improves blood flow as shown in our laboratory (AUA 2018 oral presentation by Kim, et al- TRANSPELVIC MAGNETIC STIMULATION (TPMS) AS A NOVEL THERAPY TO ENHANCE PENILE MICRO AND MACRO CIRCULATION, J Urology, Vol. 199, No. 4S, Supplement, Saturday, May 19, 2018), and higher intensity (30-50% amplitude-based on the amplitude that results in patient feeling the muscle activity) helps muscle regeneration and function by minimizing post-injury inflammation, atrophy and scar formation. Based on these observations, we hypothesize that TPMS: (a) will prevent pelvic floor muscle atrophy and result in improved strength and (b) will decrease muscle fibrosis by improving penile and pelvic muscles blood flow leading to accelerated recovery after injury. TPMS has been employed as a nonsurgical intervention for stress UI in females since 1998. For treatment with TPMS, an embedded magnetic coil positioned on the chair generates pulsed electromagnetic fields that can penetrate into the pelvic floor muscles, leading to nerve stimulation and muscle contractions. Pelvic floor muscle blood flow can be non-invasively measured simultaneously using Doppler probe placed on the penile skin as is done routinely for clinical diagnosis. Pelvic floor muscle changes can be non-invasively measured by MR imaging. The proposed mechanism is to increase pelvic muscle strength and endurance through repetitive contractions. Proposed TPMS may result in increased urethral pressure and may strengthen muscles to prevent venous leak. Non-invasive TPMS has several advantages and has never been tried in post-prostatectomy patients.

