Feasibility Outcomes: We will estimate: 1) Numbers of potentially eligible patients, number invited, number attending a pre-operative assessment clinic and consent rates (target recruitment is 24 or 3 participants per month over an initial 8-month recruitment period). 2) Patient concerns about the proposed therapy sessions/week and study duration. 3) Feasibility of recruiting in other clinics in which staff are interested in participating in a future main trial. 4) Retention, acceptability rates including response to treatment, questionnaires and imaging. 5) Intervention fidelity and adherence using study coordinator-completed case responses. 6) Determining the sexual function and continence improvement by assessing and comparing sensitivity to change. 7) Participant satisfaction with the interventions on a rating (Likert) scale. 8) Participant confidence to undergo a longer duration TPMS study. 9) Identification of barriers and enablers to adherence. 10) Establishment of outcome measures that best reflects the participants' rehabilitation goals.

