
Possible Risks: Based on available literature (see references in section 7) it is unlikely that TPMS will result in any other complications suggested by the reviewer.

Abbreviations used in the figure/text: LSCI- Laser speckle contrast imaging; PW - Pad weight, rMS- Repetitive magnetic stimulation, TPMS- Transpelvic pelvic magnetic stimulation, UI - Urinary incontinence, UTE- Ultrashort echo time, UPP- Urethral pressure profile, LPP- Leak point pressure, HDM- High definition manometery, DTI- Diffusion tensor imaging and UTI-Urinary tract infections.

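### Adverse effects are monitored for IRB reporting, but no listed outcome or planned analysis counts them by arm; one standard question and one descriptive table would close the gap

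*Combined protocol and SAP*

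**What the plan says.** Item 9.9, the data safety monitoring plan printed under Section 9.8, commits the team as follows: "We will monitor for any adverse effects and report these to the IRB within 5 days". It then sets notification rules for deaths, serious adverse events and serious problems that are both unanticipated and related. It names no other use for the information.

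The outcome list in Section 9 runs from "Feasibility Outcomes: We will estimate: 1) Numbers of potentially eligible patients" to "10) Establishment of outcome measures that best reflects the" participants' goals. The entry nearest to tolerability is item 4: "Retention, acceptability rates including response to treatment, questionnaires and imaging".

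The Data Analysis & Interpretation text in Section 9 sets its direction: "The primary aims of our data analytic strategy will be directed toward the adherence, retention and any guidance to inform modification of our method". It says the results should support "informed decisions regarding whether it is worthwhile to commit additional resources to future treatment development".

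On risk, Section 7 states that "TPMS does not cause adverse effects but improves muscle function", and the Possible Risks paragraph of Section 9 says, on the basis of literature, that "it is unlikely that TPMS will result in any other complications suggested by the reviewer". Section 15 asks, when applicable, for the type of safety data, its frequency, cumulative review, analysis and suspension conditions. The answer is that the devices carry no added risk, followed by confidentiality measures. Sections 9.4 and 14 do disclose slight tingling. Section 9.4 calls the use off-label, and Section 7 says it is new in men after prostatectomy.

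**The concern.** A feasibility trial that is meant to inform a decision on a larger one would normally report how many men in each arm had an adverse effect. Followed as written, this plan would deliver recruitment, retention, satisfaction, symptom and imaging results, with no planned adverse-effect count. The sham arm, which would help separate device effects from ordinary postoperative complaints, would have no planned use for safety.

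The timing matters because of collection. A table can be added at the analysis stage, but answers that were never asked for cannot be recovered. The visible text does not say who asks about adverse effects, how, or at which visits. The operator at the sessions knows the allocation, so an arm comparison built later could partly reflect unequal asking.

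**Working it through.** The plan states no adverse-effect rate or safety calculation, so there is no figure to reproduce. The check is a reading of the visible text, followed by the precision that a count would have.

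**1. The ten outcomes in Section 9**

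| Item | Subject | Counts men with adverse effects? |
|---|---|---|
| 1 | Eligibility, invitation, consent numbers | No |
| 2 | Concerns about sessions and duration | Indirect only |
| 3 | Recruiting in other clinics | No |
| 4 | Retention and acceptability | Indirect only |
| 5 | Fidelity and adherence, from coordinator case responses | Indirect only |
| 6 | Sensitivity to change in sexual function and continence | No |
| 7 | Satisfaction (Likert) | Indirect only |
| 8 | Confidence about a longer study | No |
| 9 | Barriers and enablers | Indirect only |
| 10 | Choice of outcome measures | No |

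Result: ten outcomes, none of them adverse effects.

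**2. The analysis text.** It plans coding of interviews, descriptive statistics, baseline comparisons, missing-data and dropout analyses, analysis of variance, mixed models and mediation. The interviews and the dropout analysis could bring tolerability problems to light. Neither yields a number of affected men per arm.

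**3. Section 15.** Of the five prompts (a) to (e), the answer addresses none directly.

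**4. Precision of a complete count.** Inputs: 20 men allocated 1:1, so 10 per arm (Section 9). The exact (Clopper-Pearson) two-sided 95% upper limit with zero events is 1 − 0.025^(1/n).

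- n = 10: 1 − 0.025^(1/10) = 0.308, so 0% to 31%.
- n = 9, one man lost (the plan expects dropout below 10%): 1 − 0.025^(1/9) = 0.336, so 0% to 34%.
- n = 2, the preliminary subjects in Sections 7 and 9, if neither had an adverse effect (an assumption; the text says only that treatment was tolerated well): 1 − 0.025^(1/2) = 0.842, so 0% to 84%.

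The chance of seeing at least one affected man among 10 is 1 − (1 − p)^10. The documents give no rate, so p is assumed over a range.

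- p = 5%: 40%
- p = 10%: 65%
- p = 20%: 89%

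**5. Whether a test is worth planning.** Fisher's exact test at 10 v 10 gives p = 0.087 for 4 v 0 and p = 0.033 for 5 v 0. Against a zero count in the other arm, only five or more affected men would reach 0.05. Counts with intervals are the right output, not a comparison.

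**The case against.** The strongest reply is that the missing outcome line is not what limits the trial. Item 9.9 promises monitoring of any adverse effect in a sham-controlled study, so counts by arm could be tabulated afterwards, and ten men per arm give a wide interval however well the question is asked. This stands. A reader might infer that the trial cannot check its own no-risk premise. The documents do not support that: the information may be gathered, and the binding limit on precision is the sample size.

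Second, the plan has other channels: interviews, coordinator case responses, acceptability, satisfaction and dropout analysis. Section 9 also keeps the coordinator who gives treatment out of assessment. These points narrow the gap but do not close it. None produces a count per arm, and keeping the operator out of assessment does not settle who asks about adverse effects.

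Third, Section 15 applies only where applicable, and the device is judged non-significant risk. That supports a light remedy. It does not show that the prompts can be skipped, because the no-risk premise is the point in question for an off-label use that the plan itself calls new in this population.

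Fourth, a reader might infer that nobody reviews accumulating events and that no pause rule exists. SOP Document 67, the attached timeline and the case forms are not in the reviewed text and may cover both. Nor does anything in the documents show that events would be under-recorded, so no size can be put on that.

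**Conclusion.** The point holds as a modest gap in what the trial plans to collect and report. Adverse effects have a route to the IRB but no place among the outcomes and no planned count by arm. A table assembled later would rest on unstandardised capture with an unblinded operator present. Standard asking would make the count interpretable without making it precise: 0 of 10 would still leave rates up to 31% open, so the table is descriptive only.

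Continence, erectile, blood-flow and MRI results are unaffected, and nothing here is evidence of harm. The conclusion rests on the outcome list, analysis text, item 9.9 and Section 15, all of which are visible, and on 10 men per arm. The 5% to 20% event rates are illustrative assumptions.

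**What to change.** - **Section 9, outcomes:** add adverse effects as an eleventh outcome. Every man in both arms completes the same short written open question at each treatment visit and at weeks 4, 8, 13 and 24. The form also records date, severity and whether the session was stopped. Answers are kept from those scoring the questionnaires, Doppler and MRI, and go to whoever makes the IRB reports.
- **Section 9, analysis:** report the number and percentage of men in each arm with any, any serious, and any session-stopping adverse effect, with exact 95% intervals and no test.
- **Item 9.9:** keep the existing notification rules. Only if SOP Document 67 does not already do so, state who reviews the cumulative list and when, and what event pauses treatment.

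Cost: one short form at visits already planned (2 per week × 12 weeks = 24 treatment visits, plus the four assessments) and one descriptive table. No new visit, test or committee is needed. The downside is a small risk that a man's answers hint at his arm, which is why the question is written and kept from the scorers.
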